5.1.2 Exclusion Criteria

Patients who meet any of the following criteria will be excluded from study entry:

1. Patients with primary central nervous system (CNS) lymphoma;
2. Any of the following laboratory abnormalities:
 - Absolute neutrophil count $<1.0 \times 10^9/L$
 - Hemoglobin $< 80 \text{ g/L}$
 - Platelets $<50 \times 10^9/L$

NOTE: In the dose expansion stage, patients with cell counts below the thresholds listed above may be considered eligible if, in the investigator's opinion, the reason is bone marrow infiltration. The investigator will discuss the eligibility of such patients with the sponsor, and only upon approval by the sponsor will a patient with cell counts below the thresholds be enrolled in the study.

NOTE: In the dose expansion stage, patients with \leq Grade 2 neutropenia per CTCAE version 5.0 and/or thrombocytopenia and with confirmed bone marrow infiltration are eligible.

3. Inadequate organ function, defined by the following:
 - Total bilirubin >1.5 times the upper limit of normal (\times ULN), with the following exception:
 - Patients with known Gilbert's disease who have serum total and direct bilirubin level $\leq 2.5 \times$ ULN and normal AST and ALT can be enrolled.

- AST or ALT $> 2.5 \times$ ULN, with the following exception:
 - In the dose expansion stage, patients with documented disease infiltration of the liver may have AST and ALT levels $\leq 5 \times$ ULN.
 - Estimated creatinine clearance (CrCl) per Cockcroft-Gault
 - Dose escalation stage of trial (Stage 1) – CrCl < 40 mL/min
 - Dose expansion stage of trial (Stage 2) – CrCl < 30 mL/min
4. International normalized ratio (INR) $> 1.5 \times$ ULN, activated partial thromboplastin time (aPTT) $> 1.5 \times$ ULN;
- Patients requiring anticoagulation therapy but with a stable INR within the recommended range according to the local guideline are eligible.
- NOTE: Patients may be considered for this study if kidney function is impaired but this impairment is believed to be a result of the patient's underlying disease. The investigator will discuss the eligibility of such patients with the sponsor, and only upon approval by the sponsor will a patient with impaired kidney function due to underlying disease be enrolled in the study.
5. Serum amylase or lipase $> ULN$ at screening or known medical history of serum amylase or lipase $> ULN$;
- NOTE: Patients with known medical history of serum amylase or lipase $> ULN$ are eligible in the dose expansion stage.

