5.4.1 During Dose Limiting Toxicities Assessment Window

If a patient experiences a DLT, dosing of HMPL-689 will be interrupted and supportive therapy administered as required in accordance with local practice/guidelines. Refer to Section 6.8 for toxicity management recommendations.

Patients who experience a DLT may resume dosing at the same or previous lower dose level at the discretion of the treating physician given that the toxicity is resolved or improved to the baseline level. If a patient experiences an intolerable toxicity at the reduced dose level, he/she will be discontinued from the study treatment. Patient cannot be dose-reduced by more than 2 dose levels. Once reduced, the dose cannot be re-escalated.

No dose reduction in patients without DLT is permitted in the DLT assessment window without the sponsor's approval.

5.4.2 After Dose Limiting Toxicities Assessment Window of Stage 1 or at Stage 2

After DLT assessment window of Stage 1 or at Stage 2, the dose of HMPL-689 may be interrupted if any of the following is observed:

- Any grade pulmonary toxicity
- Any grade diarrhea/colitis
- Grade 3 or 4 hematologic toxicity
- Grade 3 or 4 non-hematologic toxicity (except for alopecia and skin eruption, nausea, vomiting, diarrhea or constipation if well-controlled by systemic or topical medication)

Refer to Section 6.8 for detailed toxicity management recommendations for potential class-related toxicities and dose modification of HMPL-689.

For all other toxicities, treatment with HMPL-689 should be withheld until the toxicity resolves to CTCAE Grade ≤ 2 . Dosing may then be resumed at either the same dose level or the previously evaluated lower dose level if the toxicity is improved to CTCAE Grade ≤ 2 within 2 weeks, per investigator's discretion. If treatment is resumed at the same dose, and the patient experiences the same toxicity of Grade 3 or 4, the dose should be reduced following resolution of the event. If the patient continues to experience intolerable toxicity, a second dose reduction to a previously evaluated lower dose is permitted.

In all cases, every patient is allowed to reduce HMPL-689 dose only twice. If a patient continues to experience intolerable toxicity after 2 dose reductions, or if dosing with HMPL-689 is interrupted for >14 consecutive days due to toxicity (except for those with additional guidance provided in Section 6.8), treatment should be discontinued, unless otherwise agreed by the investigator and the sponsor.

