6.2.3 Protocol-Defined Adverse Events of Special Interest Expedited Adverse Events

- Non-serious AEs of special interest are required to be reported by the investigator to the sponsor immediately (i.e., no more than 24 hours after learning of the event; see Section 6.3.1 for reporting instructions).
- Adverse events of special interest for this study include: Cases of potential drug-induced liver injury (DILI) that include an elevated ALT or AST in combination with either an elevated bilirubin or clinical jaundice, as defined by Hy's law (see Section 6.3.1.5 and Appendix 14), and non-serious cases of interstitial lung disease/pneumonitis (see Section 6.8, Table 6).
- Please refer to the latest IB for additional information.

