6.3.1.5 Abnormal Liver Function Test Results

The finding of an elevated ALT or AST in combination with either an elevated total bilirubin ($\geq 2\times$ ULN) or clinical jaundice in the absence of cholestasis or other causes of hyperbilirubinemia is considered to be an indicator of severe liver injury (as defined by Hy’s law). Briefly, Hy’s Law cases have the following three components:

1. The drug causes hepatocellular injury, generally shown by a higher incidence of 3-fold or greater elevations above the ULN of ALT or AST than the (non-hepatotoxic) control drug or placebo;
2. Among trial patients showing such AT elevations, often with ATs $>3\times$ ULN, one or more patients also show elevation of serum TBL to $>2\times$ ULN, without initial findings of cholestasis (elevated serum ALP);
3. No other reason can be found to explain the combination of increased AT and TBL, such as viral hepatitis A, B, or C; preexisting or acute liver disease; or another drug capable of causing the observed injury.

Therefore, investigators must report as an AE in the occurrence of either of the following:

- Treatment-emergent ALT or AST $\geq 3\times$ ULN in combination with total bilirubin $\geq 2\times$ ULN; or
- Treatment-emergent ALT or AST $\geq 3\times$ ULN, in combination with clinical jaundice.

The most appropriate diagnosis or (if a diagnosis cannot be established) the abnormal laboratory values should be recorded on the Adverse Event CRF (see Section 6.3.1.4) and reported to the sponsor’s designee as a non-serious AE of special interest (see Section 6.2.3).

The guidance on diagnosis and management of hepatic AEs (including Hy’s law) can be found in Section 6.8, Table 8.

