6.8 HMPL-689 Dose Modification and Toxicity Management Algorithm for Clinical Trials

This section provides guidance to the investigators for the differential diagnosis and management of the important potential class toxicities noted on HMPL-689 trials and/or those associated with other PI3K δ inhibitors. This constitutes general recommendations to investigators involved in HMPL-689 studies and should be supplemented with any additional protocol-specific guidance. In case of questions, prompt discussions with the sponsor's clinical representative are recommended. Please see [Table 6](#), [Table 7](#), [Table 8](#), [Table 9](#), [Table 10](#), [Table 11](#), and [Table 12](#) for the dose modification and toxicity management recommendations for pulmonary AEs (including pneumonia/pneumonitis), diarrhea/colitis, hepatic AEs, infection, neutropenia, thrombocytopenia, and rash and cutaneous skin reactions, respectively.

As a general principle, the recommendations are as follows:

- Differential diagnosis for any adverse event should be diligently evaluated according to standard medical practices.
- Recommendations provided here should be evaluated in conjunction with the local clinical standard of care, and overall management plan should be based on the investigator's best clinical judgment.
- Consultation with specialty medical care is recommended as appropriate and especially prior to any invasive diagnostic or therapeutic procedures.

Table 6 Dose Modification/Toxicity Management Recommendations for Pulmonary Adverse Events Including Pneumonia/Pneumonitis

Adverse Reaction CTCAE V5.0 Grade/Severity	Recommended Management	Recommended Dosing Modification	Recommended Follow-up

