Grade 3 AST/ALT elevation (>5 to 20 times ULN or from baseline, if baseline is abnormal)	
 Evaluate differential diagnosis and causality (including pre-existing liver disease and infectious etiology) Close monitoring for any clinical symptoms Weekly monitoring of transaminase and bilirubin levels until return to Grade 1 or <3 times ULN Consider hepatic consult and treat accordingly per standard treatment guidelines Permanently discontinue study drug if the patient meets the definition of Hy's law 
 AST or ALT value > 3 × ULN and TBL > 2 × ULN No other reason to explain combination of increased AST or ALT and TBL, ALP normal (i.e., no initial findings of cholestasis) 	Withhold study drug	
 If resolved to Grade 1 or baseline in less than 28 days, resume study drug at the same or a reduced dose at the discretion of the investigator If not resolved to Grade 1 or baseline more than 28 days or worsens or recurs after re-initiating therapy, permanently discontinue study drug If likely immune mediated, seek hepatic consult and consider use of steroids with gradual taper
Grade ≥4 (>20 times ULN or from baseline, if baseline is abnormal)	
Evaluate differential diagnosis and causality (including pre-existing liver disease and infectious etiology) Consider hepatic consult and treat accordingly per standard treatment guidelines If the AST/ALT and bilirubin levels meet the definition of Hy's law, permanently discontinue the study drug
	Permanently discontinue study drug	
 Continue close follow-up until resolution If likely immune mediated, seek hepatic consult and consider use of steroids with gradual taper

ALP = alkaline phosphatase; ALT = alanine aminotransferase; AST = aspartate aminotransferase; COVID-19 = coronavirus 2019; CTCAE = Common Terminology Criteria for Adverse Events; RT-PCR = real-time polymerase chain reaction; TBL = total bilirubin level; ULN = upper limit of normal.

Table 9 Dose Modification/Toxicity Management Recommendations for Infection

Adverse Reaction CTCAE V5.0 Grade/Severity	Recommended Management	Recommended Dosing Modification	Recommended Follow-up

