17.4. LABORATORY EVALUATIONS

Laboratory evaluations will be performed in the site laboratory. Laboratory evaluations to be included in the outputs are included in the protocol, section 5.7.10, including hematology, chemistry panel, serum amylase and lipase, fasting lipid profile, coagulation, thyroid hormones, serum β -2 microglobulin, viral serology, urinalysis, leukocyte immunophenotyping, pregnancy testing, serum immunoglobulins assessment from the study site's local laboratory. All laboratory results (including pregnancy test results) will be included in listings.

Laboratory results will be converted to International Standard Units (SI Units), and all the analysis and presentation will be based on SI units.

The incidence of patients with the following elevations abnormal liver function tests (Hy's Law) at post-baseline will also be summarized:

- ALT or AST >3 x ULN and <= 5 x ULN (based on the worst post-baseline case)
- ALT or AST > 5 x ULN (based on the worst post-baseline case)
- Total bilirubin >= 2 x ULN (based on the worst post-baseline case)
- (ALT or AST >3 x ULN) and total bilirubin >= 2 x ULN [defined as total bilirubin increase by >= 2 x ULN within 14 days after ALT or AST increase by > 3 x ULN]
- Hy's law: (AST or ALT >3 x ULN) and total bilirubin >= 2 x ULN and ALP < 2 x ULN [defined as total bilirubin increase by >= 2 x ULN and ALP increase <2 x ULN within 14 days after ALT or AST increase by > 3 x ULN]

All laboratory evaluation records and abnormal liver function will be listed.

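### Table 8 makes normal ALP a condition of the Grade 3 Hy's law stop, but SAP 17.4 counts Hy's law up to ALP <2 × ULN, so a tabulated Grade 3 case may be restarted

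*Protocol*

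**What the plan says.** **Protocol Section 6.8, Table 8, Grade 3 row** (AST/ALT >5 to 20 × ULN, or × baseline if baseline is abnormal). The default is to withhold drug. A permanent stop is recommended for Hy's law, which the row defines itself: AST or ALT >3 × ULN, total bilirubin (TBL) >2 × ULN, no alternative explanation, and "ALP normal (i.e., no initial findings of cholestasis". Otherwise the follow-up column applies: "If resolved to Grade 1 or baseline in less than 28 days, resume study drug at the same or a reduced dose", at the investigator's discretion.

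**Protocol Section 6.3.1.5**, component 2 of its Hy's law list, describes the bilirubin rise as "without initial findings of cholestasis (elevated serum ALP". Elevated ALP is thus the mark of cholestasis, and no multiple of ULN is allowed for. The reporting trigger in the same section (ALT or AST ≥3 × ULN with TBL ≥2 × ULN, or with jaundice) has no ALP condition.

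**SAP Section 17.4** counts Hy's law when AST or ALT is >3 × ULN with "total bilirubin >= 2 x ULN and ALP < 2 x ULN", the bilirubin rise falling within 14 days of the AST/ALT rise. It has no causality condition. SAP Section 2 states that the SAP is based on Amendment 5, so both texts are current.

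**Protocol Section 5.4.2** requires discontinuation after more than 14 consecutive days of interruption for toxicity, "except for those with additional guidance provided in Section 6.8".

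**The concern.** The protocol intends a permanent stop for Hy's law, but the stop and the safety table use different ALP limits. A Grade 3 patient whose ALP is mildly raised at onset falls between them. The final analysis will label the patient a Hy's law case, while the row that governs dosing lets the drug be restarted, even at the same dose.

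Mildly raised ALP is not screened out by number. Exclusion criterion 3 (Section 5.1.2) limits bilirubin, AST/ALT and creatinine clearance but not ALP, and it relaxes the AST/ALT limit for some patients: "In the dose expansion stage, patients with documented disease infiltration of the liver may have AST and ALT levels" up to 5 × ULN. A patient who enters with ALP above ULN may never satisfy a normal-ALP condition.

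What is at stake is re-exposure after an unexplained combined transaminase and bilirubin rise. Only patients still on treatment under Amendment 5 are affected.

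**Working it through.** The plan gives no figure to reproduce. The check compares two logical rules.

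**Inputs** (all in × ULN; normal ALP read as ≤1 at onset; no other explanation; bilirubin rise within 14 days):

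- Table 8 Grade 3 stop: AT >3 and TBL >2 and ALP ≤1
- SAP 17.4 Hy's law: AT >3 and TBL ≥2 and ALP <2
- Section 6.3.1.5 reporting trigger: AT ≥3 and TBL ≥2

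Here AT is the higher of AST and ALT. With a normal baseline every Grade 3 case has AT >5, so the AT limb is always met and the rules differ only in TBL and ALP.

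**Single case: ALT 8, TBL 2.5, ALP 1.5.** SAP: 8 >3, 2.5 ≥2, 1.5 <2, so Hy's law. Table 8: 8 >3 and 2.5 >2, but 1.5 is not ≤1, so no permanent stop; withhold and possibly resume.

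**Illustrative grid.** ALT 5.1, 8, 12, 20; TBL 1.5, 2.0, 2.5, 5; ALP 0.8, 1.0, 1.2, 1.5, 1.9, 2.0, 2.5. That is 4 × 4 × 7 = 112 combinations.

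| TBL | ALP | Combinations | SAP Hy's law | Table 8 stop |
|---|---|---|---|---|
| 1.5 | any | 4 × 1 × 7 = 28 | no | no |
| 2.0 | 0.8, 1.0 | 4 × 1 × 2 = 8 | yes | no |
| 2.0 | 1.2 to 1.9 | 4 × 1 × 3 = 12 | yes | no |
| 2.5, 5 | 0.8, 1.0 | 4 × 2 × 2 = 16 | yes | yes |
| 2.5, 5 | 1.2 to 1.9 | 4 × 2 × 3 = 24 | yes | no |
| 2.0, 2.5, 5 | 2.0, 2.5 | 4 × 3 × 2 = 24 | no | no |

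The SAP rule is met by 8 + 12 + 16 + 24 = 60 and the Table 8 stop by 16, leaving 60 − 16 = 44 between them: 24 through ALP alone, 12 through ALP together with TBL of exactly 2.0, and 8 through TBL of exactly 2.0 alone. All 44 meet the reporting trigger. These counts depend on the chosen grid and are not frequencies.

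**Effect of the change.** With ALP <2 and TBL ≥2 in the Grade 3 row, all 60 stop. The gap goes from 44 to 0 on the stated assumptions, and none of the 16 existing stops is lost.

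**Abnormal baseline.** The row then covers 5 × 2.5 = 12.5 to 20 × 2.5 = 50 × ULN for a baseline of 2.5 × ULN, and 5 × 5 = 25 to 20 × 5 = 100 × ULN for a baseline of 5 × ULN. In patients with liver infiltration the disease itself may be another explanation, and then the stop does not apply.

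**Do other provisions close the gap?**

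- *Section 5.4.2, more than 14 days:* no, because toxicities covered by Section 6.8 are exempt.
- *Section 5.8.3.1 (Stage 1):* partly. Dosing stops if a DLT has not returned to Grade 1 or lower, or a later DLT equivalent has not resolved, within 14 days, and no Section 6.8 exemption is stated. Faster resolution is not covered. Section 5.8.3.2 (expansion) has no such time limit.
- *Table 8, Grade 1 or 2 row:* partly. Its Hy's law stop is worded on AST/ALT and bilirubin only. With a normal baseline, a patient returning toward Grade 1 passes through AT >3 to 5 × ULN. If TBL is still raised then, the literal wording stops the drug whatever the ALP.
- *Reporting and oversight:* Section 6.2.3 says "Non-serious AEs of special interest are required to be reported by the investigator to the sponsor immediately", within 24 hours. The safety review committee can decide on an individual's continuation (Section 4.1.3), and the investigator or sponsor can withdraw the patient (Section 5.8.3). None of these prohibits a first restart.
- *Table 8, recurrence:* permanent stop, but only after re-exposure.

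**The case against.** The strongest reply is that the two rules do different jobs. SAP 17.4 is a laboratory tabulation without a causality condition; Table 8 is a clinical stop that requires other causes to be excluded. A sensitive count beside a more specific dosing rule is ordinary practice. This stands to the extent that the two need not be identical. It does not explain why an unexplained case should be stopped at ALP 1.0 × ULN and restartable at 1.5 × ULN.

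A reader might infer that nothing in Table 8 stands against a restart. That is too strong, given the Grade 1 or 2 wording and the Stage 1 rule. Snapshot combinations cannot show a patient passing back through the lower grade band.

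Section 6.8 describes its own status: "This constitutes general recommendations to investigators involved in HMPL-689 studies". Resumption is discretionary, enrollment has been halted, and each case reaches the sponsor within 24 hours. Exclusion criteria 7 and 28 let clinically significant liver disease or a worrying laboratory finding bar entry, though neither sets an ALP limit. All of this lowers the weight of the point.

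Appendix 14, which Section 6.2.3 cites for Hy's law, was not available for this review and may state an ALP limit. The Grade 3 row nevertheless writes out its own definition.

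Finally, the proposed wording leaves an unevenness. ALT 4, TBL 2.5, ALP 2.5 × ULN stops on the literal Grade 1 or 2 wording, while ALT 8 with the same TBL and ALP may still resume. That is true already, and the change does not worsen it.

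**Conclusion.** The point holds in a narrow form and is minor. For a Grade 3 case with no other explanation, TBL >2 × ULN and initial ALP above 1 but below 2 × ULN, the SAP tabulates Hy's law while Table 8 permits resumption after resolution in under 28 days. A further difference at TBL of exactly 2 × ULN is trivial. The gap remains for cases that resolve quickly and for expansion patients, unless TBL is still raised when AST/ALT re-enters the Grade 1 or 2 band.

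The conclusion assumes that normal ALP means not above ULN at onset; an ALP that is normal at first and rises later still meets Table 8. It also assumes that Appendix 14 does not override the row. The number of patients cannot be derived, and 44 of 112 must not be read as a rate. Nor do the documents support inferring that Hy's law patients in general may be restarted: with normal ALP and TBL >2 × ULN the two rules agree, and Grade 4 elevations always stop.

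**What to change.** In the Grade 3 row of Table 8, replace the normal-ALP condition with ALP <2 × ULN, keeping the reference to initial findings and the requirement that no other reason explains the case. Change TBL >2 × ULN to TBL ≥2 × ULN. Use the same two limits in component 2 of the Hy's law list in Section 6.3.1.5. Leave the ALP-free reporting trigger and the Grade 1 or 2 row as they are; adding an ALP condition there would weaken protection. Check that Appendix 14 agrees.

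The cost is one bullet in Table 8 and one line in Section 6.3.1.5, with no SAP change. It can go into the next amendment or a site clarification and does not justify an amendment of its own. The downside is a few more permanent discontinuations among patients with mildly raised ALP, some of whom may be benefiting.

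The change does not make the two rules identical. Tabulated cases with another cause will still not be stopped, and Grade 3 cases with ALP ≥2 × ULN may still resume.

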CMV = cytomegalovirus; COVID-19 = Coronavirus 2019; CTCAE = Common Terminology Criteria for Adverse Events; GI = gastrointestinal; PCR = polymerase chain reaction; PJP = *Pneumocystis jiroveci* infection; RNA = ribonucleic acid.

Table 10 Dose Modification/Toxicity Management Recommendations for Neutropenia

Adverse Reaction CTCAE V5.0 Grade/Severity	Recommended Management	Recommended Dosing Modification	Recommended Follow-up
Grade 1 or 2 Neutropenia (ANC of $\geq 1 \times 10^9/L$)	
 Monitor for any fever If persistent, consider supportive care as needed 	Continue current dose	
 In case of worsening of neutropenia or neutropenic fever, treat as Grade 3 or 4
Grade 3 Neutropenia (ANC of 0.5 to $1 \times 10^9/L$)	
 Monitor with complete blood count every 2 weeks Consider supportive care, including use of growth factors for patients with persistent or severe myelosuppression If persistent Grade 3, recurs or worsens, withhold study drug 	Continue current dose	
 On resolution to a lower grade or baseline, resume at the same dose level In case of recurrence after restarting treatment, consider next lower dose level at the discretion of the investigator In case of worsening of neutropenia or neutropenic fever, treat as Grade 4
Grade 4 Neutropenia (ANC of $< 0.5 \times 10^9/L$) OR Occurrence of neutropenic fever or infection	
 Monitor with complete blood count at least every 2 weeks Strongly recommend initiation of growth factors and other supportive care including antibiotic prophylaxis 	Withhold study drug	
 On resolution to a lower grade or baseline (ANC of $\geq 1 \times 10^9/L$), resume at the same dose level or at the next lower dose level at the discretion of the investigator (also refer to treatment guidelines for infection) In case of recurrence after restarting treatment, resume at the next lower dose level

ANC = absolute neutrophil count; CTCAE = Common Terminology Criteria for Adverse Events.

Table 11 Dose Modification/Toxicity Management Recommendations for Thrombocytopenia

Adverse Reaction CTCAE V5.0 Grade/Severity	Recommended Management	Recommended Dosing Modification	Recommended Follow-up

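### Table 10's restart rule after Grade 4 neutropenia contradicts the table's own grade limits, and its bracketed count conflicts with baseline for Stage 2 patients enrolled below that count

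*Protocol*

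**What the plan says.** All ANC values below are in units of 10⁹/L.

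- **Restart rule.** The follow-up column of the Grade 4 row in Protocol Section 6.8, Table 10 reads "On resolution to a lower grade or baseline (ANC of" at least 1), and drug is then resumed at the same dose level, with the next lower dose level as the alternative at the investigator's discretion. While the criterion is unmet, drug is withheld. Counts are required at least every 2 weeks.
- **Who enters the row.** Patients with ANC below 0.5, and also any patient with "Occurrence of neutropenic fever or infection", for whom no separate count is stated.
- **Next row up.** The heading begins "Grade 3 Neutropenia (ANC of 0.5 to" and gives 1 as the upper end. Dosing continues in this row unless the neutropenia persists, recurs or worsens. Its own restart wording uses the same two alternatives (lower grade, baseline) with no number.
- **Top row.** Grades 1 and 2 together are ANC of 1 or more.
- **Entry.** Section 5.1.2, exclusion 2 excludes ANC below 1.0. In the dose expansion stage, however, "patients with cell counts below the thresholds listed above may be considered eligible" if the investigator attributes the low count to marrow infiltration and the sponsor approves. No lower limit is attached.
- **Comparison.** Table 8 (hepatic events) defines its grades against baseline when baseline is abnormal. Table 10 has no such provision.

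**The concern.** The restart sentence offers two routes, a lower grade or baseline, and then attaches one number that does not match the first route and cannot match the second for every enrolled patient. Two sites that follow the same line carefully could restart drug at different neutrophil counts after the most severe grade of neutropenia.

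Safety is the primary endpoint of Stage 2. In the China study at the recommended dose, neutropenia was the most frequent Grade 3 or higher TEAE (13.6%, Section 2.3), so the row is likely to be used. The time off drug also feeds quantities that SAP Section 15 summarises: actual duration of treatment, dose intensity and relative dose intensity. Part of the variation in those outputs could then reflect how a site reads one sentence. Enrolment has been halted, but patients who are benefiting remain on drug, so the rule is still in use.

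**Working it through.** No sample-size or error-rate figure is involved. The check sets the restart sentence against the grade bands in the same table and against the entry criterion.

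**Step 1: the limit implied by *lower grade*.** Grade 4 is ANC < 0.5, Grade 3 is 0.5 to 1, and Grade 1 or 2 is ≥ 1. For a patient who was below 0.5, the first lower grade is Grade 3, reached at ANC = 0.5. The bracket prints 1, which is where Grade 1 or 2 begins. The printed figure is therefore not reproduced from the words. The two disagree for 0.5 ≤ ANC < 1.0.

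**Step 2: four readings of the sentence.** Each was tried with baselines of 1.5, 0.7 and 0.3:

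- A: any lower grade, so ANC ≥ 0.5
- B: the bracket governs the whole phrase, so ANC ≥ 1
- C: the bracket qualifies only *baseline*, so ANC ≥ 0.5, or ANC both ≥ baseline and ≥ 1
- D: the words without the number, so ANC ≥ 0.5 or ANC ≥ baseline

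| Baseline ANC | Current ANC | A | B | C | D |
|---|---|---|---|---|---|
| 1.5 | 0.4 | no | no | no | no |
| 1.5 | 0.7 | yes | **no** | yes | yes |
| 1.5 | 1.0 | yes | yes | yes | yes |
| 0.7 | 0.4 | no | no | no | no |
| 0.7 | 0.7 | yes | **no** | yes | yes |
| 0.7 | 1.0 | yes | yes | yes | yes |
| 0.3 | 0.3 | no | no | no | **yes** |
| 0.3 | 0.7 | yes | **no** | yes | yes |
| 0.3 | 1.0 | yes | yes | yes | yes |

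At a current ANC of 0.7, reading B gives the opposite answer to the other three, whatever the baseline.

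**Step 3: patients enrolled below 1.0.**

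- Baseline 0.5 to < 1.0: the lower-grade limit is met at the patient's own baseline. Only the bracket conflicts, because it asks for a count above baseline.
- Baseline < 0.5, possible only because the note sets no floor: a patient back at baseline meets neither 0.5 nor 1. Only the word *baseline*, read without the bracket, is satisfied.

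**Step 4: what changes downstream.** Assume a site checks counts only at the 2-week minimum. Missing the limit at one check can then add about 14 days off drug. Under the SAP Section 15 formulas, 14 further zero-dose days before the last dose reduce actual duration by 14 / 30.4375 = 0.46 months. Over an exposure of 6 months (6 × 30.4375 = 182.6 days), at an otherwise constant planned dose, relative dose intensity falls by 14 / 182.6 = 7.7 percentage points. More frequent counts would make both figures smaller.

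Protocol Section 5.4.2 also ends treatment after more than 14 consecutive days' interruption for toxicity, unless Section 6.8 gives additional guidance or the investigator and sponsor agree otherwise. Table 10 states no time limit, so whether that exception covers neutropenia is not clear from the text.

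**The case against.** **The bracket may have a purpose.** A patient who enters the row through neutropenic fever while at Grade 3 has ANC ≥ 1 as the next lower grade, and 1.0 is also the normal entry threshold. The general rule in Section 5.4.2 uses Grade 2 or lower, which by Table 10's bands is also ANC ≥ 1. These are plausible explanations of where the number came from, but the sentence does not limit it to febrile patients or to *baseline*, and the Section 5.4.2 rule is for toxicities other than those handled in Section 6.8. The inconsistency for a patient recovering from below 0.5 stands.

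**Section 6.8 is guidance.** It defers to investigator judgment and invites discussion with the sponsor, so some variation between sites is accepted. This limits the seriousness. It does not make a self-contradicting criterion useful to the person exercising that judgment.

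**Readers might infer more than the text supports:**

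- *That the rule states two numerical limits.* It prints one. The 0.5 follows from *lower grade* together with the grade bands.
- *That neither limit fits anyone with a low baseline.* This is true only for a baseline below 0.5. The documents do not show that any such patient was enrolled, and each would have needed sponsor approval.
- *That a patient enrolled below 0.5 triggers withholding at the first count.* Table 10 grades adverse reactions. Section 6.3.1.8 treats a pre-existing condition as an adverse event only if it worsens, and Section 7.3.2.2 requires onset or worsening on or after first dose. An unchanged baseline count does not qualify.
- *That the count of TEAEs leading to interruption becomes site-dependent.* SAP Section 17.2 identifies these by the recorded action of interrupting drug, whatever count is later used to restart.

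**Conclusion.** Wrong as written. For a patient recovering from an ANC below 0.5, the Grade 4 restart sentence is both met and not met throughout 0.5 to < 1.0, and no other part of the protocol settles which applies. Separately, the bracket cannot be reconciled with *baseline* for a Stage 2 patient enrolled below 1.0.

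The effect is on the restart decision, and through it on patient safety, interruption length, actual treatment duration and dose intensity. The number of patients affected cannot be estimated: no Grade 4 neutropenia rate is given, the 13.6% is for Grade 3 or higher in another study, and the number enrolled under the exclusion note is not stated. The 14-day illustration assumes counts at the minimum frequency. The conclusion itself rests only on Table 10's bands and the exclusion 2 note. It takes no view on which count should govern.

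**What to change.** The sponsor should reconcile the Grade 4 restart sentence with the grade bands in the same table and with the note to exclusion 2, so that a single criterion is stated. The wording should say how *baseline* is applied to patients enrolled below the count thresholds, and whether the bracketed number covers every patient in the row or only some. The value is for the sponsor's clinicians to decide.

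The cost is about one line in Table 10, issued as a clarification to sites with active patients. No analysis in the SAP needs to change. The clarification cannot alter restarts already made.
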